- 1) Mediastinal chest tube output must be ≤ 3 ml/kg/hr and 2 ml/kg/hr the first and second hour respectively, and 1 ml/kg/hr thereafter.
- 2) Hemodynamically stable.
- 3) Urine output ≥ 1 ml/kg/hr.
- 4) Normothermia ($>36^{\circ}\text{C}$)
- 5) Respiratory parameters fulfilled
 - pH ≥ 7.35 and ≤ 7.55
 - PaCO₂ ≥ 30 mmHg and ≤ 50 mmHg
 - PaO₂ ≥ 80 mmHg
 - SpO₂ $\geq 92\%$

Respiratory rate $\leq 25/\text{min}$

Discharge from the intensive care unit and hospital criteria

Current conventional discharge from the intensive care unit criteria and hospital will be used.

ICU discharge time will be recorded and traditionally assumes following criteria:

- Alert and cooperative
- No inotropic support
- No hemodynamically unstable dysrhythmia
- Adequate respiratory status
- Minimal chest tube drainage
- Urine output $\geq 0.5 \text{ ml/kg/hr}$

Discharge from the hospital will be recorded and traditionally assumes following criteria:

- Hemodynamically stable
- Stable cardiac rhythm
- Noninfected incisions
- Afebrile
- Ability to void and bowel movements
- Independent ambulation and feeding.

G. Data Collection

The following variables will be entered into a database:

1. Demographic:
 - a. Age
 - b. Sex
 - c. Society of Thoracic Surgeons (STS) risk score (where applicable)
2. Comorbidities:
 - a. History of cerebrovascular accident
 - b. History of vascular thromboembolic disease (arterial or venous thrombosis, organ ischemia secondary to thromboembolic phenomenon).
 - c. Coronary artery disease
 - d. History of atrial fibrillation
 - e. $\text{GFR} < 60 \text{ mL/min/1.73 m}^2$
3. Preoperative laboratory variables:
 - a. CBC, and the following if available preoperatively PT/ INR, APTT, Fibrinogen
4. Preoperative medications:
 - a. Anticoagulant medications
5. Intraoperative variables:
 - a. Procedure performed

- b. Initial or Redo-Sternotomy
 - c. Cardiopulmonary bypass time
 - d. Aortic cross clamp time (if applicable)?
 - e. Presence and (if present) duration of deep hypothermic circulatory arrest
 - f. Allogenic blood product utilization after cardiopulmonary bypass
 - g. Laboratory variables (CBC, PT/ INR, APTT, and Fibrinogen)
 - h. Anticoagulant (Heparin +/- other) and anti-fibrinolytic use (aminocaproic acid or tranexamic acid)
 - i. Direct transfusion related complications/reactions
 - 1. TRALI (Transfusion related acute lung injury) by standard definition¹⁶
 - 2. ABO/Non-ABO hemolytic reaction
 - 3. Anaphylactic or Allergic reaction

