Power Analysis was determined from a study by Arnekian et al that retrospectively presented a reduction in blood loss in patients receiving PCC over those receiving FFP.² In that study, the distribution of 24-hr chest tube drainage was highly skewed, but the observed difference between the two groups was at least 0.65 standard deviation units. Using a non-parametric test, a sample-size of **N=50 per group should provide statistical power of >85% to detect a difference of this magnitude. Therefore we suggest a sample-size of at least 50 per group.** In the paper, they also found a dramatic difference in ICU red cell transfusions. If the true difference is as large as they observed a sample-size of N=50 per group would also provide adequate statistical power for this endpoint.²

Primary endpoints in this study will be units of allogenic blood product administration, and 24 hour postoperative blood loss. Exploratory endpoints will include rate of serious adverse outcomes.

Baseline patient characteristics, including demographics, comorbidities, preoperative laboratory values, and cardiovascular variables will be reported and compared across treatment groups. Categorical variables will be reported as counts and percentages, and compared across groups using chi-square or Fisher's exact tests. Continuous variables will be reported as median and interquartile ranges, and compared across groups using Wilcoxon rank sum tests.

K. Feasibility and Time Frame

This study with the combined collaboration of divisions of anesthesiology and cardiovascular surgery is quite feasible. Approximately 2200-2500 cardiopulmonary bypass procedures are done annually at St. Mary's Hospital. Making the conservative estimate that 50% will consent 1000 patients should be consented within 1 year. Given that approximately 11% of patients

receive transfusion; this would result in approximately 100-110 patients to be treated within 12 months. We expect to get IRB approval within the next one month. The study and data collection will take about 1 year with approximately two months for data analysis.

L. Strengths and Limitations

Strengths: This will be the first prospective randomized controlled trial in the United States directly assessing the effect of PCC compared to FFP in the setting of postcardiac surgery coagulopathy and bleeding in patients undergoing elective cardiac surgery.

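### Section 3.J plans only unadjusted tests and no effect estimate for the two primary endpoints, although plausibly prognostic pre-randomisation variables are collected and only about one in ten randomised patients is compared

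*Combined protocol and SAP*

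**What the plan says.** Section 3.J is the whole of the statistical plan. It defines two primaries: "Primary endpoints in this study will be units of allogenic blood product administration, and 24 hour postoperative blood loss". For power it states "the distribution of 24-hr chest tube drainage was highly skewed", that "the observed difference between the two groups was at least 0.65 standard deviation units", and that "N=50 per group should provide statistical power of >85% to detect a difference of this magnitude". The test behind that figure is described only as non-parametric.

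The next paragraph opens "Baseline patient characteristics, including demographics, comorbidities, preoperative laboratory values, and cardiovascular variables will be reported and compared across treatment groups" and goes on to name chi-square or Fisher's exact tests for categorical variables. For the rest it says "Continuous variables will be reported as median and interquartile ranges, and compared across groups using Wilcoxon rank sum tests". No sentence ties a named test to either primary endpoint. No adjusted or stratified analysis, effect estimate or confidence interval appears in the document.

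Three other sections bear on the point:

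- **3.C and 3.D:** patients are randomised at consent, before surgery, in blocks stratified by surgical procedure. About 1000 are to be consented so that 100 are treated.
- **3.G:** the database holds the preoperative blood count, bypass time, circulatory arrest, laboratory values and "Initial or Redo-Sternotomy".
- **3.D:** the allocation is disclosed to the anaesthesiologist at a time that is not given, and surgical and intensive care staff are not blinded.

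**The concern.** The trial stops at 50 treated patients per arm, and the power statement uses 50 per group, so by inference the treated patients are the ones compared. They are about a tenth of those randomised. Blocks and procedure strata balance the full randomised group, and that balance need not carry over to the tenth who go on to bleed and meet the laboratory criteria.

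The plan will compare baseline variables between arms but does not say what follows if they differ. That leaves adjustment open to choice after the results are seen. The protocol's own background and transfusion rules make some preoperative values plausibly prognostic: section 1 lists thrombocytopenia among the causes of post-bypass bleeding, and section 3.E ties red cell transfusion to a haemoglobin threshold.

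At stake are power at a fixed sample size, a treatment contrast free of chance differences in measured risk, and an estimate that a reader can interpret. A median, an interquartile range and a p-value do not supply the last of these.

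**Working it through.** **Inputs.** From 3.C, 3.E and 3.J: 50 per arm, difference 0.65 SD, non-parametric test. (Section 2 says 100 per arm; 50 is used because 3.C, 3.E, 3.J and 3.P all give it.) Assumed: two-sided alpha 0.05, which is not stated, and R², the share of outcome variance explained by the covariates, which is not in the documents.

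**1. The plan's own figure.** Power = Φ(δ·√(n·ARE/2) − 1.96), where ARE is the efficiency of Wilcoxon relative to the t-test.

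- ARE = 3/π (normal shape): 0.65 × √(47.75/2) = 3.176; Φ(1.216) = 0.888.
- ARE = 0.864 (worst case): 0.65 × √(43.2/2) = 3.021; Φ(1.061) = 0.856.

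The stated figure of more than 85% is reproduced.

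**2. Gain from adjustment, by formula.** Replace n by n/(1 − R²). This ignores the degrees of freedom spent.

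| Difference | R² = 0 | 0.10 | 0.20 | 0.30 |
|---|---|---|---|---|
| 0.65 SD | 0.888 | 0.917 | 0.944 | 0.967 |
| 0.50 SD | 0.685 | 0.731 | 0.780 | 0.831 |

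**3. Gain with four covariates, by simulation.** Settings: 50 per arm, outcome normal on a suitable scale, four independent covariates jointly explaining R², rank ANCOVA against unadjusted Wilcoxon. Two sets of runs agreed to about one point (one of them used 6,000 runs per setting); ranges cover both.

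| Difference | Wilcoxon | R² = 0.10 | 0.20 | 0.30 |
|---|---|---|---|---|
| 0.65 SD | about 0.88 | 0.89-0.90 | 0.92-0.93 | 0.95-0.96 |
| 0.50 SD | about 0.68 | 0.70-0.71 | 0.75-0.76 | 0.80 |

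At R² of 0.05 or less there is no material gain. With covariates that explain nothing, the loss is 1 to 2 points (0.86 against 0.87 at 0.65 SD; 0.66 against 0.68 at 0.50 SD).

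**4. Chance imbalance.** The standard error of a standardised difference is √(2/50) = 0.2.

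- P(difference above 0.3 SD) = 2(1 − Φ(0.3/0.2)) = 2(1 − Φ(1.5)) = 0.134 for one covariate.
- For at least one of four independent covariates: 1 − 0.866⁴ = 0.44.
- A 0.3 SD imbalance in a covariate (or combined risk score) that explains R² of the variance shifts the unadjusted contrast by 0.3·√R². That is 0.095, 0.134 and 0.164 SD at R² 0.10, 0.20 and 0.30, or 15%, 21% and 25% of 0.65 SD.

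**5. Validity of the unadjusted test.** With no true difference, its simulated rejection rate was 4.2% to 5.6%, consistent with the nominal 5%.

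**6. Which covariates are safe.** Redo status and procedure stratum are settled before randomisation, although 3.G lists sternotomy type among intraoperative items. The preoperative blood count precedes surgery. Bypass time and post-protamine laboratory values arise after randomisation, under unblinded care with some discretionary steps such as additional protamine (3.E). Being measured before study product is therefore not enough to make them safe.

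**The case against.** The strongest case against has four parts.

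- **The text does not assign the test.** The Wilcoxon sentence sits in a paragraph about baseline characteristics, so a reader might infer that the plan expressly prescribes it for the primaries. It does not. This part stands. But the power paragraph assumes a non-parametric test and Wilcoxon is the only one named. If it was not intended, the primary analysis is unspecified and 3.J needs the same edit.
- **The unadjusted test is sound.** A reader might infer inflated type I error or an invalid comparison. The simulation shows neither. Nor do the baseline significance tests affect the primaries, since no adjustment rule is attached to them.
- **The gain is assumed.** No predictor strength is given anywhere, so calling the covariates strong or the power free is unsupported. At 0.65 SD the unadjusted test already exceeds 85%. A longer list costs more: with seven covariates, rank ANCOVA gave 0.87 at R² 0 and 0.89 at 0.10. This stands, and it argues for a short list.
- **Later covariates could mislead.** A reader might infer that anything measured before product is a legitimate covariate. The protocol does not support this, because disclosure of allocation is undated and staff are unblinded. This stands and limits the primary model to pre-randomisation variables.

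None of this answers the missing effect estimate and interval, or the weak balance in the treated subset.

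**Conclusion.** The point holds as a matter of precision and prespecification, not of validity. Section 3.J has no adjusted analysis, effect estimate or confidence interval for either primary, while usable pre-randomisation variables are at hand and about nine in ten randomised patients drop out of the comparison.

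For blood loss at the planned 0.65 SD, adjustment is worth roughly 1 to 8 points of power for R² between 0.10 and 0.30. At 0.50 SD it is worth roughly 2 to 12. The smaller effect deserves attention because 0.65 SD comes from a retrospective comparison. At R² of 0.05 or less adjustment gains nothing and may cost 1 to 2 points. Separately, a given covariate has a 13% chance of differing by more than 0.3 SD.

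These figures assume two-sided 0.05, 50 per arm, a difference of 0.65 or 0.50 SD on a scale where the outcome is near normal, and entry to the treated group unrelated to arm. The gain for units transfused was not simulated, so no figure is claimed for that endpoint.

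**What to change.** In 3.J, state the primary analyses explicitly:

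- **24-hour blood loss:** rank ANCOVA, or ANCOVA on log volume.
- **Total units:** a proportional-odds model.
- **Covariates in both:** procedure stratum, redo sternotomy, and preoperative haemoglobin and platelet count. Define the strata and keep them few, since each category uses a degree of freedom. Define which preoperative blood count is used.
- **Optional:** body weight. It must be known for dosing but is not listed in 3.G, so a field would be needed. FFP is dosed per kg, so a common weight slope may not fit the units model in both arms and should be checked.
- **Reporting:** the adjusted effect with a 95% confidence interval for each primary. For blood loss analysed by ranks, name the effect measure that goes with the test.
- **Sensitivity analyses:** the unadjusted Wilcoxon test, and a model adding bypass time and post-bypass laboratory values. Those later variables may enter the primary model only if allocation is documented as concealed until they are measured.

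The cost is plan wording, a few degrees of freedom and a rule for a few missing covariate values. No extra patients are needed, and no new data unless weight is added.

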Prothrombin complex concentrate
compared to fresh frozen plasma for
post-cardiopulmonary bypass
coagulopathy and bleeding, a
prospective randomized trial at large US
medical center

NCT02557672

11/2/2020

November 2, 2020, protocol version 7.6

Prothrombin complex concentrate compared to fresh frozen plasma for post-cardiopulmonary bypass coagulopathy and bleeding, a prospective randomized trial at large US medical center.

Principal Investigators: [name] M.D¹, [name].¹

Co-investigators:

[REDACTED]

¹Department of Anesthesiology
²Division of Cardiovascular Surgery

Abstract

Background:

Post-cardiopulmonary bypass coagulopathy and bleeding represents one of the largest areas of blood product transfusion in surgical practices today. Abnormal bleeding after cardiopulmonary bypass has been shown to be present in about 11% patients.¹ Current literature shows lower transfusion rate and blood loss in patients receiving prothrombin complex concentrate (PCC) when compared to fresh frozen plasma (FFP) after cardiac surgery.²

Specific Aim:

Determine best practice in management of postcardiopulmonary bypass coagulopathy and bleeding. Our aim is to compare administration of PCC (Kcentra) to FFP for patients with post bypass factor mediated coagulopathy and clinically significant microvascular bleeding. Primary endpoints for the study will be allogenic blood product transfusion rate and 24 hour postoperative blood loss.

Hypothesis:

Patients receiving PCC (Kcentra) will have same or decreased allogenic blood product transfusion rate and blood loss after cardiac surgery compared to patients receiving fresh frozen plasma.

Significance:

This will be the first prospective randomized controlled clinical trial directly comparing PCC to FFP for post cardiopulmonary bypass microvascular bleeding and factor-mediated coagulopathy.

1. Background and Significance:

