substantial. In addition, massive bleeding after cardiac surgery is associated with higher rates of reoperation, morbidity, and mortality.³ Current practice per our institutional transfusion algorithm is to use fresh frozen plasma as first line therapy for factor mediated coagulopathy and bleeding after cardiopulmonary bypass.

Large prospective randomized studies directly comparing PCC to FFP in the setting of factor-mediated bleeding after cardiac surgery have not been conducted.

We hypothesize that PCC use will show a reduction in allogenic transfusion requirements in cardiac surgical patients with factor mediated postcardiopulmonary bypass bleeding.

2. Specific Aims:

Our aim is to conduct a prospective randomized controlled trial of patients undergoing elective cardiac surgery. We plan to preoperatively consent and enroll sufficient patients to reach a goal of 200 randomized patients (100 patients per arm) that demonstrate clinically significant microvascular bleeding and factor mediated coagulopathy after cardiopulmonary bypass. Randomized patients with clinically significant factor mediated bleeding will receive transfusion of PCC (Kcentra) (100 patients) or fresh frozen plasma (100 patients). Factor mediated coagulopathy will be defined per our current transfusion algorithm as PT >16.6 sec/ INR >1.6 sec. Primary outcome measures for efficacy will be total units of allogenic blood product transfused, and 24 hour postoperative blood loss. Outcome measure for safety will be rate of serious adverse outcomes. Analysis of coagulation factor levels will also be conducted prior to cardiopulmonary bypass, post cardiopulmonary bypass, and after product administration (PCC or FFP).

Hypothesis:

PCC arm will have same or decreased allogenic blood product transfusion rate and blood loss after cardiac surgery compared to patients receiving fresh frozen plasma.

3. Research Design and Methods:

A. Study Overview

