Limitations: If the study demonstrates lower transfusion requirements and blood loss in the PCC arm, further studies will need to address optimal dosing requirements. Current PCC dosing is based on INR and weight for patients on warfarin therapy. Should no difference be found between groups, or lower transfusion rate and/or postsurgical blood loss is found in the FFP arm, the question as to whether this represents a superior result of FFP or underdosing of the PCC arm will remain.

M. Anticipated Results

- a. PCC administration will reduce the amount of allogenic blood product transfused and amount of postoperative bleeding in patients undergoing cardiac surgery.
- b. Adverse event rate will be similar between the 2 treatment arms, representing the known risk associated with cardiovascular surgery.
- c. Perioperative transfusion related costs will be similar or lower in patients receiving PCC compared with FFP

N. Estimated Costs

Kcentra will be supplied and funded by CSL Behring (Melbourne, Australia). FFP if administered will be covered by the patient/payer as this treatment is the current practice standard. All laboratory testing not routine to this patient population will be funded by CSL Behring and is outline within the budget.

O. Research Materials

All data forms will be stored in individual patients study folders and handled securely for patient confidentiality. This data will be entered into an access database that is password protected.

P. Human Subjects

We will obtain informed consent from all participants prior to initiation of the study. Informed consent will meet the requirements of the code of federal regulations 21CFR 50.25 (elements of informed consent) and the IRB of this center. During informed consent for the study cardiac

surgical patients will be told that the chance of needing a transfusion in the perioperative period is around 11%. Should they meet criteria by our current transfusion algorithm to receive FFP, they would have been randomized to receive either FFP or the study PCC infusion. A copy of the consent form will be placed in the patient's medical records. The study will be stopped when 50 patients have received treatment in each study arm. Efficacy will be defined as either a statistically significant reduction in transfusion of allogenic blood products or 24 hour postoperative blood loss. Safety will be defined as similar rate of serious adverse outcomes in the PCC study drug arm to the standard therapy FFP arm.

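### Efficacy may be claimed on either of two primary endpoints, but the plan states no alpha, sidedness, testing order or multiplicity method, so the chance of a false claim is undefined and can be up to twice that of a single test

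*Combined protocol and SAP*

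**What the plan says.** Section 3.J names two primary endpoints: "Primary endpoints in this study will be units of allogenic blood product administration, and 24 hour postoperative blood loss". Section 2 agrees: "Primary outcome measures for efficacy will be total units of allogenic blood product transfused, and 24 hour postoperative blood loss". Neither says how the two combine into a conclusion. That rule appears only in 3.P (Human Subjects): "Efficacy will be defined as either a statistically significant reduction in transfusion of allogenic blood products or 24 hour postoperative blood loss".

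The statements of hypothesis are not uniform:

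- The Abstract and section 2 name both endpoints joined by *and*. Section 2 reads "PCC arm will have same or decreased allogenic blood product transfusion rate and blood loss after cardiac surgery".
- The anticipated result in 3.M does the same: "PCC administration will reduce the amount of allogenic blood product transfused and amount of postoperative bleeding in patients undergoing cardiac surgery".
- The last paragraph of section 1 states a hypothesis about transfusion requirements alone.

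On power, 3.J assumes a blood-loss difference of at least 0.65 SD and a non-parametric test, and concludes that "N=50 per group should provide statistical power of >85% to detect a difference of this magnitude". No alpha accompanies that figure. For transfusion, 3.J gives no power figure. It says only that power would be adequate, and refers to ICU red cells rather than total units. The Wilcoxon rank sum test is named only in the paragraph on baseline characteristics.

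**The concern.** An either/or rule over two endpoints is a union test. If PCC reduces neither outcome, a chance finding on either one still counts as efficacy. The plan could control this by splitting alpha, by ordering the tests, or by requiring both endpoints to succeed. It does none of these, and without a stated alpha or sidedness the error rate of the rule cannot be worked out from the documents.

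This matters most when the results are mixed. If one endpoint has a nominal p below 0.05 and the other misses, 3.P calls the trial a success, and there is no prespecified error rate with which to defend that claim. Nor can a reader tell which alpha lies behind the power figure.

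**Working it through.** **Inputs from the documents.** Two primary endpoints (2, 3.J); the either/or rule (3.P); 0.65 SD, 50 per group and power above 85% with a non-parametric test (3.J).

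**Assumptions, because the documents are silent.** Per-test level: two-sided 0.05 or one-sided 0.05. Correlation between the endpoint test statistics: 0, 0.5 and 0.8.

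**Step 1: reproduce the plan's power.** Noncentral t, with noncentrality 0.65 × √(n × E / 2), where n = 50 and E is the efficiency of the Wilcoxon test relative to the t-test: 0.864 (worst case), 0.955 (normal data) or 1.0. For E = 0.955 this is 0.65 × √23.875 = 3.18.

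| Level per test | E = 0.864 | E = 0.955 | E = 1.0 |
|---|---|---|---|
| two-sided 0.05 | 84.8% | 88.2% | 89.6% |
| one-sided 0.05 | 91.2% | 93.4% | 94.3% |
| two-sided 0.025 | 76.9% | 81.4% | 83.3% |

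Simulated Wilcoxon tests on normal data (20,000 runs) give 87.9% at two-sided 0.05 and 81.1% at 0.025. The stated figure therefore reproduces at an unadjusted two-sided 0.05. It is also consistent with one-sided 0.05, so it does not reveal which was meant.

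**Step 2: false claim of a reduction under the either/or rule.** With chance *a* per endpoint in the favourable direction and critical value *z*, the rate is 2*a* − P(both statistics beyond *z*), from the bivariate normal distribution.

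| Level per test | Correlation 0 | 0.5 | 0.8 | Upper bound | One endpoint |
|---|---|---|---|---|---|
| two-sided 0.05 (*a* = 0.025, *z* = 1.960) | 0.05 − 0.0006 = 4.9% | 0.05 − 0.0046 = 4.5% | 0.05 − 0.0110 = 3.9% | 5% | 2.5% |
| one-sided 0.05 (*a* = 0.05, *z* = 1.645) | 0.10 − 0.0025 = 9.75% | 0.10 − 0.0122 = 8.8% | 0.10 − 0.0248 = 7.5% | 10% | 5% |
| Holm first step (*a* = 0.0125, *z* = 2.241) | 0.025 − 0.0002 = 2.5% | 0.025 − 0.0018 = 2.3% | 0.025 − 0.0049 = 2.0% | 2.5% | – |

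Simulated Wilcoxon tests under the null (50 per arm, 20,000 runs) give 4.9%, 4.4% and 4.0% for the first row, and 2.5%, 2.3% and 2.1% for the full Holm procedure.

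**Step 3: sensitivity of the power cost.** Step 1 assumes a normal shift, but 3.J says of the source study that "the distribution of 24-hr chest tube drainage was highly skewed". Under assumed lognormal shifts of 0.65 SD at 50 per arm, Wilcoxon power at 0.025 is about 86–99% depending on the degree of skew (about 95% at a log-SD of 0.5). Sample size also matters. Section 2 plans 100 per arm, whereas 3.C, 3.E and 3.P stop at 50 treated per arm. At 100 per arm, the step 1 formula gives 98–99% at 0.025.

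**The case against.** The best defence is that the hypotheses are directional ("PCC arm will have same or decreased allogenic blood product transfusion rate and blood loss after cardiac surgery"), so an overall one-sided 5% standard may be intended. Two-sided 0.05 per endpoint would then already meet it, because its bound is 5%. That arithmetic is right, but no section states such a standard. If the directional wording instead meant one-sided 0.05 per test, the bound would be 10%.

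A second defence is that blood loss and transfusion are likely to be positively correlated, which reduces the inflation. It does, but at a correlation of 0.8 the rate is still 3.9% against 2.5%.

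A third concerns cost: skewed data, or 100 per arm, would make the loss of power from adjustment small. This stands, and it is why the 81% figure must be conditional. It bears on the price of the remedy, not on the error rate.

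Three stronger readings are tempting, and the documents do not support them:

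- A reader might infer that the trial definitely runs at a 5% (or 10%) false-claim rate. Those rates follow from assumed alphas; the plan states none.
- A reader might infer that the *and* in the hypotheses makes both endpoints necessary, so that 3.P contradicts them. Naming two endpoints together is not a decision rule, and section 1 also states a hypothesis on transfusion alone.
- A reader might infer that the stated power is wrong. It reproduces; only its alpha is missing.

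**Conclusion.** The point holds. The only efficacy rule in the plan is either/or across two primary endpoints, with alpha, sidedness, testing order and multiplicity all unspecified. The firm conclusion, free of any assumed level, is that the rule can up to double the false-claim rate of a single endpoint tested at the same level. The particular rates (up to 5% against 2.5%, or up to 10% against 5%) rest on assumed per-test levels and on correlations from 0 to 0.8. They do not depend on whether 50 or 100 per arm is correct; the power figures do. Because this rule decides whether efficacy is claimed, it should be settled in the plan.

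**What to change.** Put the same text in 3.J and 3.P, for example:

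> Each primary endpoint (total allogeneic units; 24-hour blood loss) is compared between arms with a two-sided Wilcoxon rank sum test. Holm's procedure holds the overall two-sided type I error at 0.05: the smaller p-value is tested at 0.025 and, if significant, the larger at 0.05. Efficacy is claimed only for an endpoint that passes and favours PCC.

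For units transfused, the Wilcoxon test is a new choice that the sponsor should confirm, because 3.J ties its non-parametric test to the blood-loss calculation.

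State the alpha behind the power figure. At 50 per arm and 0.65 SD under a normal shift, blood-loss power is about 88% (85–90%) at two-sided 0.05 and about 81% (77–83%) at the 0.025 step, and higher if the outcome is skewed. First reconcile section 2 (100 per arm) with 3.C, 3.E and 3.P (50 treated per arm), since these figures depend on it.

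The cost is wording and a modest loss of blood-loss power at the first Holm step, with no extra patients.

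A fixed sequence with blood loss first would keep the stated power, but it is not recommended: if blood loss failed, the transfusion hypothesis in section 1 could not be claimed. No power figure for transfusion is offered, because the documents give no effect size for total units.

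### Section 3.P lets one improved primary endpoint establish efficacy with no condition on the other, so a split result would be labelled effective against the trial's formal hypothesis

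*Combined protocol and SAP*

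**What the plan says.** - **Endpoints.** Section 3.J: "Primary endpoints in this study will be units of allogenic blood product administration, and 24 hour postoperative blood loss". No hierarchy is given between the two.
- **Efficacy rule.** Section 3.P: "Efficacy will be defined as either a statistically significant reduction in transfusion of allogenic blood products or 24 hour postoperative blood loss".
- **Formal hypothesis.** Section 2: "PCC arm will have same or decreased allogenic blood product transfusion rate and blood loss after cardiac surgery", compared with FFP. The Abstract says nearly the same.
- **Second hypothesis.** The end of Section 1 speaks of transfusion only: "We hypothesize that PCC use will show a reduction in allogenic transfusion requirements in cardiac surgical patients".
- **Expectation.** Section 3.M, item a: "PCC administration will reduce the amount of allogenic blood product transfused and amount of postoperative bleeding in patients undergoing cardiac surgery".
- **Reading of a result that favours FFP.** Section 3.L says that if "lower transfusion rate and/or postsurgical blood loss is found in the FFP arm", it stays open whether FFP is superior or PCC was underdosed.
- **Safety criterion.** Section 3.P: "Safety will be defined as similar rate of serious adverse outcomes in the PCC study drug arm to the standard therapy FFP arm". The serious adverse events listed in Section 3.G do not include 24-hour blood loss.

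No section adds a condition on the second primary endpoint. No significance level, sidedness or non-inferiority margin is stated.

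**The concern.** The formal hypothesis is a statement about both endpoints together, while the efficacy rule is met by either one alone. The mismatch does not depend on the significance level: at any alpha, a significantly adverse result on the second primary does not alter the label that Section 3.P assigns.

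The two endpoints could part company by design. Under Section 3.E, patients treated in the FFP arm receive FFP by assignment, while PCC-arm patients receive it only if bleeding and abnormal tests persist. If randomised FFP counts towards allogenic units, which the text implies but does not state, units can fall simply because PCC replaces the first plasma dose. Chest tube output measures bleeding directly. The gap is symmetric: efficacy could also rest on blood loss while transfusion is worse.

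At stake is how a split result is reported. With no rule written beforehand, its handling would be settled after the data are seen.

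**Working it through.** **1. The passages side by side**

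| Result with PCC | Section 3.P | Formal hypothesis | Section 3.L |
|---|---|---|---|
| Fewer units, less blood loss | effective | supported | not triggered |
| Fewer units, blood loss not significantly different | effective | not refuted, sameness not shown | not triggered |
| Fewer units, significantly more blood loss | effective | refuted | FFP superior or PCC underdosed |
| Significantly more units, less blood loss | effective | refuted | FFP superior or PCC underdosed |

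The last two rows give one dataset incompatible labels.

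**2. The plan's own power figure**

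From Section 3.J: 50 per group, 0.65 SD, a non-parametric test, power above 85%. Assumed: Wilcoxon rank sum, two-sided 0.05.

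Power = Φ(d·√(n/2 · ARE) − 1.960), where ARE is the efficiency of the Wilcoxon test relative to the t-test.

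- ARE 0.955 (normal data): 0.65 × √(25 × 0.955) = 3.176; Φ(1.216) = 88.8%.
- ARE 0.864 (worst case): 0.65 × √(25 × 0.864) = 3.021; Φ(1.061) = 85.6%.

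The stated figure reproduces, so sample size is not the issue.

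**3. How often the labels conflict, simple model**

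Assume PCC lowers transfusion by 0.65 SD. For independent endpoints, P(conflict) = P(units significantly lower) × P(blood loss significantly higher). The last column comes from a bivariate-normal simulation.

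| True blood loss with PCC | Independent endpoints | Correlation 0 to 0.9 |
|---|---|---|
| 0.65 SD worse | 0.888 × 0.888 = 78.9% | 77.6–78.9% |
| 0.4 SD worse | 0.888 × 0.498 = 44.2% | 38.6–44.2% |
| unchanged | 0.888 × 0.025 = 2.2% | 0.1–2.2% |

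If the reduction in units were certain, the unchanged row would be 1 × 0.025 = 2.5%, the ceiling. If neither endpoint differs, the figure is 2 × 0.025 × 0.025 = 0.13%.

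**4. Same question with unit counts**

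Assumed, since the documents give no unit distribution or rescue rate: 3–5 FFP units per dose, other units with mean 4, rank-sum tests, 50 per arm, blood loss truly 0.65 SD worse with PCC. Ranges reflect repeated simulations with differing assumptions about the spread of other units; in the last row they run over the correlation, from 0.3 to 0.7.

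| Other units in the PCC arm | FFP rescue 20% | 50% | 80% |
|---|---|---|---|
| same as the FFP arm | 87–90% | 65–71% | 15–16% |
| one extra per patient | 75–78% | 29–32% | 1–3% |
| two extra per patient | 48–51% | 6–10% | 0–1% |
| driven by bleeding (latent correlation 0.3 to 0.7) | 83–53% | 40–5% | 3–0% |

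**5. The guarded rule** (one significant reduction, the other not significantly worse)

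- PCC truly better on both by 0.65 SD: power 98.8% to 92.2% over correlation 0 to 0.9, as under the current rule.
- Other endpoint truly unaffected: at most about 2.5% of efficacy claims blocked, for endpoints that are independent or positively correlated.
- Opposed by 0.65 SD: efficacy claims fall from 88.8% to 9.9–11.2%.
- Blood loss truly 0.3 SD worse, 20% rescue: P(significantly worse) = Φ(0.3 × 4.886 − 1.960) = Φ(−0.494) = 31%. A reduction in units is then almost certain, so efficacy is still declared in about 69% of trials.

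A real test of sameness needs a margin m. With one-sided 0.025, 85% power and true difference 0, n per arm = 2(1.960 + 1.036)²/m². For assumed margins of 0.3, 0.4, 0.5 and 0.65 SD this gives 200, 113, 72 and 43.

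**The case against.** An at-least-one-endpoint rule is a legitimate design choice. Section 1 hypothesises a transfusion reduction alone, and a transfusion-only success fits it. Section 3.M lists anticipated results, not decision criteria. Section 3.L shows that the investigators foresaw FFP doing better on one endpoint and said how they would read it. Both endpoints are primary, so both results would be in view, and the 3.P sentence does not govern stopping, which depends on the number treated.

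Much of this stands. The conflict is with the formal hypothesis in the Abstract and Section 2, not with every hypothesis in the document. Section 3.M is supporting context only. But Section 3.L is interpretive and does not restrict 3.P, so the efficacy label would still be assigned.

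A reader might infer that the trial is likely to declare efficacy for a product under which patients bleed more, at a rate near 87%. The documents do not support that. The figure requires a true harm opposite to the plan's premise of lower blood loss with PCC, a low rescue rate, and other units unaffected by the extra bleeding. The last assumption sits badly with Sections 3.E and 3.F, where persistent bleeding and hemoglobin drive further transfusion.

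**Conclusion.** The point holds as a gap in the decision rule. Section 3.P would label a significantly split result effective, while the formal hypothesis would be refuted and Section 3.L would leave FFP superiority or PCC underdosing open.

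It is not a likely chance error: at most about 2.5% of trials unless the true effects are opposed. If units fall and blood loss is 0.65 SD worse, the chance of a contradictory declaration lies anywhere from near 0% to about 90%. That range rests on assumed rescue rates, unit distributions and the link between bleeding and units, on two-sided 0.05 Wilcoxon tests, and on randomised FFP counting as allogenic units. No single value in it should be quoted as the expected rate.

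The rule should be corrected before analysis, because the correction is nearly free. The sample size and the stated power are not in question here.

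**What to change.** In Section 3.P, define efficacy as a significant reduction in at least one primary endpoint **and** no significant increase in the other in the PCC arm. State the two-sided significance level, since a one-sided test for reduction cannot flag an increase. Report discordant primaries as mixed, with no efficacy claim, and present the effect estimate and confidence interval for both endpoints whatever the outcome. Align the wording of Sections 3.L and 3.M, and say whether randomised FFP counts in total allogenic units.

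State plainly that this is a minimum safeguard: the absence of a significant increase with 50 per arm does not establish sameness. That claim would need a non-inferiority margin, which the documents do not give, and possibly more patients.

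The cost is wording only. Power is unchanged if PCC helps both endpoints, and at most about 2.5% of efficacy claims are blocked if the other endpoint is truly unaffected.
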